7.6.2.1 Analysis of clinical equivalence of test and reference treatments

To show the clinical equivalence, estimates of mean percent change from baseline in the inflammatory and non-inflammatory lesion counts will be calculated for the Test and Reference treatment, and then the 90% CI for the mean ratio will be constructed using Fieller's method. Bioequivalence will be established if the 90% confidence intervals for the

ratios of Test/Reference means are contained within the interval [0.80, 1.25] for the PP population for both lesion types (inflammatory and non-inflammatory).

To this end, first an ANOVA model will be fit (separately for each lesion type) with percent change from baseline in lesion count as outcome and treatment, center and treatment-by-center interaction as factors on the data from Test and Reference treatments only (excluding Vehicle subjects). If the treatment-by-center interaction factor is not significant at the 0.05 level, the model will be rerun without the interaction term. Treatment means and standard errors will be estimated from this model. Then Fieller's formula will be applied; covariance between the treatment means will be assumed to be 0. See [Appendix 11.2](#) for complete description of the Fieller's formula.

A non-parametric rank based ANOVA will be considered when the data is highly skewed. The evaluation of skewness, (using SAS[®] PROC UNIVARIATE) will be performed using the residuals from ANOVA and if the skewness statistic is less than -2 or greater than +2, the analysis will be performed on the ranks of the percent change in the inflammatory lesion count values.

Analysis of bioequivalence will be performed on the PP population

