10.3.3.2 Test of Clinical Equivalence

The evaluations of clinical equivalence will be performed for the PP population.

For the primary efficacy assessment, the two-sided, 90% confidence interval on the test/reference ratio of the mean percent change from screening/baseline to week 12 in each lesion type will be calculated using Fieller's method and the pooled variance estimate (MSE) obtained from a two-way Analysis of Variance (ANOVA) of the Test and Reference results. The statistical model for the ANOVA will contain terms for treatment and center. If the skewness of the residuals from the ANOVA is outside of -2 to 2, then a nonparametric approach will be used to obtain the confidence intervals. Bioequivalence will be established if the 90% confidence intervals for the ratio of test/reference means, for both inflammatory and non-inflammatory lesion counts, are contained within the interval [0.80, 1.25] using the per protocol (PP) population.

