5. HYPOTHESES TESTING

Hypothesis of Equivalence

A two-sided, 90% confidence intervals on the test/reference ratio for mean percent change from Baseline in the inflammatory and non-inflammatory lesion counts will be constructed using Fieller's method. The estimates of treatment means and standard errors will be obtained from a two-way Analysis of Variance (ANOVA) of the Test and Reference results, using a statistical model containing terms for treatment and center. Non-parametric methods will be considered if the skewness factor for the residuals from the ANOVA model is outside the range -2 to +2.

Bioequivalence will be established if the 90% confidence intervals for the ratios of test/reference means for both the inflammatory and non-inflammatory lesions are contained within the interval [0.80, 1.25].

Hypothesis of Superiority

The null hypothesis to be tested is that there is no difference in the mean percent change (reduction) from baseline in the inflammatory and non-inflammatory lesion counts between the active treatment and the Vehicle treatment. The hypothesis testing will be performed separately for the Test treatment versus the Vehicle treatment and for the Reference treatment versus the Vehicle treatment using ANOVA under assumption of normal error and homogeneity of variance. Only data for the relevant two treatment arms will be included in each ANOVA. Similarly to bioequivalence, non-parametric methods will be considered if the skewness factor for the residuals from the ANOVA model is outside the range -2 to +2.

Superiority will be established if the mean percent change (reduction) from Baseline in both the inflammatory and non-inflammatory lesion count for each active treatment is greater than, and statistically different from ($p < 0.05$, two-sided), that for the Vehicle.

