7.6.2.2 Analysis of superiority to vehicle control

The analysis of superiority will be performed separately for the Test treatment versus the Vehicle treatment and for the Reference treatment versus the Vehicle treatment and separately for the inflammatory and non-inflammatory lesions. Each of these analyses will be performed using an ANOVA model with percent change from baseline in the lesion count as outcome and treatment, center and treatment-by-center interaction as factors. If the treatment-by-center interaction factor is not significant at the 0.05 level, the model will be rerun without the interaction term. The model will be fit on data from the Test and Vehicle treatment for analysis of superiority of the Test treatment and separately on data from the Reference and Vehicle treatment for analysis of superiority of the Reference treatment. From this model, the least square (LS) mean estimate for each treatment group with the 95% CI will be calculated; further, an estimate of the LS mean difference between the active treatment (Test or

Reference) and Vehicle with 95% CI and the p-value for test of no difference will be calculated.

Superiority will be established if the mean percent change from Baseline (reduction) for each active treatment and each lesion type is estimated to be greater than, and statistically significantly different from ($p < 0.05$ for test of no difference) that for the Vehicle, for the mITT population.

Analysis of superiority will be performed on the mITT population.

A non-parametric rank-based ANOVA will be considered under the same circumstances as for the analysis of bioequivalence.

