8. CHANGES FROM PROTOCOL-SPECIFIED ANALYSES

The definition of the mITT population was expanded in the SAP.

Otherwise, there are no changes from the protocol-specified analyses.

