11.2 Code Fragments

ANOVA model for superiority analysis in the primary endpoint

```
proc glm data=<datasets name>;  
  by lesion_type;  
  class <treatment> <center>;  
  model <Percent change from baseline in lesion count at week 12> = <treatment> <center>  
  <treatment>*< center>/ ss3;  
  lsmeans <treatment> / pdiff cl;  
  output out=residuals residual=residual;  
run;  
quit;
```

Note: this analysis needs to be performed separately for test and reference treatments on a dataset containing only test and vehicle or reference and vehicle treatment subjects. If treatment-by-center interaction term is not significant at 0.05 level, the model will be rerun without this term.

Analysis of clinical equivalence in the primary endpoint

ANOVA model:

```
proc glm data=<datasets name>;  
  by lesion_type;  
  class <treatment> <center>;
```

```

model <Percent change from baseline in lesion count at week 12> = <treatment> <center>
<treatment>*<center>/ ss3;
lsmeans <treatment> / stderr;
output out=residuals residual=residual;

run;
quit;

```

Here dataset contains test and reference treatment subjects only.

Note: if the treatment-by-center interaction term is not significant at the 0.05 level, the model will be rerun without this term.

Fieller's method.

Generally, Fieller's formula allows to calculate the confidence interval for the ratio of two (possibly correlated) means of two samples a and b with expectations μ_a and μ_b , and variances $\nu_{11}\sigma^2$ and $\nu_{22}\sigma^2$ and covariance $\nu_{12}\sigma^2$. If $\nu_{11}, \nu_{12}, \nu_{22}$ are all known, then a $(1 - 2\alpha)$ confidence interval (mL, mU) for μ_a/μ_b is given by

$$(m_L, m_U) = \frac{1}{(1 - g)} \left[\frac{a}{b} - \frac{g\nu_{12}}{\nu_{22}} \mp \frac{t_{r,\alpha}s}{b} \sqrt{\nu_{11} - 2\frac{a}{b}\nu_{12} + \frac{a^2}{b^2}\nu_{22} - g \left(\nu_{11} - \frac{\nu_{12}^2}{\nu_{22}} \right)} \right]$$

where

$$g = \frac{t_{r,\alpha}^2 s^2 \nu_{22}}{b^2}.$$

Here s^2 is an unbiased estimator of σ^2 based on r degrees of freedom, and $t_{r,\alpha}$ is the α -level deviate from the Student's t-distribution based on r degrees of freedom.

In the case of this study the two samples are independent (different subjects), thus covariance can be assumed to be zero, and the formula simplifies to:

$$(m_L, m_U) = \frac{1}{1-g} \left[\frac{m_t}{m_r} \mp \frac{t_{r,\alpha}}{m_r} \sqrt{se_t^2 + \frac{m_t^2}{m_r^2} se_r^2 - g \cdot se_t^2} \right]$$

where

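### SAP 7.6.2 lets an interaction pre-test choose the primary ANOVA, while the protocol (and SAP section 5 for equivalence) fixes it as treatment plus center, and SAP section 8 does not declare the change

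*SAP*

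**What the plan says.** **Protocol.** Section 10.3.3.2 (equivalence) states: "The statistical model for the ANOVA will contain terms for treatment and center". Section 10.3.3.3 says the same for superiority. Neither mentions an interaction.

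**SAP section 5.** For equivalence, the means and standard errors come from an ANOVA "using a statistical model containing terms for treatment and center". For superiority, section 5 says ANOVA and lists no model terms.

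**SAP 7.6.2.1 and 7.6.2.2.** Both start from a model with "treatment, center and treatment-by-center interaction as factors". The rule that follows is: "If the treatment-by-center interaction factor is not significant at the 0.05 level, the model will be rerun without the interaction term". For equivalence, "Treatment means and standard errors will be estimated from this model", meaning whichever model is left after the pre-test, and these feed Fieller's formula. The code in 11.2 carries the interaction in both models and requests "lsmeans <treatment> / stderr" for equivalence, with SAS default weighting.

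**SAP section 8.** It reports an expanded mITT definition, then says: "Otherwise, there are no changes from the protocol-specified analyses".

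**The concern.** Two specifications of the definitive analysis are in force. For equivalence the SAP disagrees with itself as well as with the protocol. For superiority the disagreement is between SAP 7.6.2.2 and protocol 10.3.3.3. The section that should record the departure says there is none.

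The two specifications can give different answers. In the additive model the treatment contrast is precision-weighted across centers. With the interaction kept, LS means at the default weighting give every pooled center the same weight, whatever its size. A p-value for a different hypothesis therefore decides which contrast is reported and with what standard error. The SAP does not say how a kept interaction is to be interpreted, and it does not retain the additive result as primary. Bioequivalence needs both lesion types to pass, so a switch in one model can decide the trial. If the two models then disagreed, each would have support in the documents.

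**Working it through.** There is no sponsor figure to reproduce, because sample size, means, SDs, allocation and the pooling rule are redacted.

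**Inputs from the documents.** Pre-test level 0.05. Two equivalence models (two lesion types) and four superiority models (two comparisons by two lesion types). 90% Fieller interval within [0.80, 1.25], with covariance of the means set to 0.

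**Assumed inputs.** About 300 PP subjects per active arm, Test:Reference 1:1 within center, mean reduction 55%, SD 35 points, no true interaction, and five center-size layouts.

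**Step 1: how often the model switches by chance.**
- At least one of two: 1 - 0.95^2 = 0.0975. Simulated with correlated lesion types: 9.1-9.4%.
- At least one of six: 1 - 0.95^6 = 0.265 if independent. The models share arms and subjects; simulated allowing for that: 22-24%.

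**Step 2: what a switch does to precision.** With n_k subjects per arm in center k, K centers and residual variance s^2:
- Treatment + center: Var(difference) = 2s^2 / sum(n_k).
- Interaction kept: Var(difference) = (2s^2 / K^2) * sum(1/n_k).
- The ratio is the arithmetic mean of the center sizes divided by their harmonic mean, so it equals 1 when centers are equal.

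Worked case, 15 centers of 60, 50, 40, 30, 25, 20, 15, 12, 10, 8, 8, 6, 6, 6, 6 per arm: sum(n_k) = 302 and sum(1/n_k) = 1.352. The variance ratio is (302/15) * (1.352/15) = 1.81, so the SE ratio is 1.35. That equals losing 1 - 1/1.81 = 45% of the sample for this contrast.

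**Step 3: simulate the SAP's rule** (interaction F-test, then Fieller with zero covariance; 20,000 runs per scenario; one lesion type; true ratio 1.00).

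| Centers (per-arm sizes) | SE ratio, difference | Reported CI width ratio | Pass rate, treatment + center | Pass rate, SAP two-step rule | Switched trials only: treatment + center, then interaction kept |
|---|---|---|---|---|---|
| 15 equal (20) | 1.00 | 1.00 | 0.991 | 0.991 | 0.99, 0.99 |
| 15 (10-30) | 1.06 | 1.03 | 0.989 | 0.988 | 0.99, 0.97 |
| 25 (4-30) | 1.23 | 1.10 | 0.982 | 0.978 | 0.98, 0.91 |
| 15 (6-60) | 1.35 | 1.14 | 0.980 | 0.971 | 0.98, 0.80 |
| 15 (4-90) | 1.66 | 1.22 | 0.950 | 0.928 | 0.95, 0.53 |

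The 4-90 layout is an extreme that center pooling is meant to prevent, so I carry forward about 1.06 to 1.5 for the SE ratio in unequal layouts.

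In the 6-60 layout the two models reached different conclusions in 19% of switched trials, or about 0.051 * 0.1945 = 1% of all trials. A separate set of runs with centers of 6-60 per arm, less well powered under the additive model, gave a fall among switched trials from about 0.79 to 0.52.

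**Step 4: type I error at a true ratio of 0.80.** The two-step rule passed 0.016-0.051 of trials overall. Within switched trials it passed 0.048-0.089, against 0.014-0.054 for the additive model in the same trials.

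**The case against.** The strongest defense is that the pre-test is itself pre-specified. SAP 7.6.2 and 11.2 fix the threshold, the sequence and the code, leave the analyst no discretion, and end at the protocol's model about 95% of the time when there is no interaction. That is fair as a description of 7.6.2. It does not answer section 5 and the protocol, which state another model, or section 8, which says nothing else changed.

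Four stronger readings are tempting and are not supported:

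- **A large loss of power.** A reader might infer this from the interaction model's pass rates, which fall as low as 0.63 in the most unequal layout when the term is always kept. The SAP keeps it only when p<0.05. Under the rule as written, pass rates are 0.93-0.99 against 0.95-0.99, a loss of about 0-2 points.
- **Inflated type I error.** The reported interval does ignore the selection step, and error after a switch can reach about 9%. Overall it stayed at or below about 5%. One reason is that the rule that "covariance between the treatment means will be assumed to be 0" is conservative for the additive model when centers are unequal, which is a separate matter.
- **Precision always falls.** With equal pooled centers the two models give the same estimate and SE. SAP 7.6.1 pools small centers, and the redacted rule may leave little imbalance.
- **SAP section 5 contradicts 7.6.2.2 on superiority.** It lists no superiority terms; that conflict is with protocol 10.3.3.3 only.

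**Conclusion.** The inconsistency stands on unredacted text, and SAP section 8 is inaccurate on this point. As written, the primary model is not uniquely specified, and under 7.6.2 the definitive contrast and its SE depend on a pre-test.

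The practical size is modest on average and can be serious in the trials affected. Chance switching occurs in about 9-10% of trials for at least one equivalence model and about 22-26% for at least one of six. After a switch the SE of the difference is unchanged with equal pooled centers, and about 1.06 to 1.5 times larger in assumed unequal layouts, where the bioequivalence conclusion can reverse. Across all trials the cost is about 0-2 points of power, with no overall type I error above about 5%.

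The switching rates assume no true interaction. The precision and power figures also rest on assumed sample size, SD, mean reduction and center sizes, so they are illustrations, not estimates for this trial. The point should be corrected before unblinding; it does not show that the planned analysis is invalid.

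**What to change.** In SAP 7.6.2.1, 7.6.2.2 and 11.2, make treatment plus pooled center the only primary model for all six analyses, as in the protocol. Report the treatment-by-center p-value and by-center estimates as supportive results that do not alter the primary model. It would also help to name the model terms for superiority in SAP section 5.

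The cost is SAP wording and one term removed from two code fragments; no new data are needed. The downside is that a real interaction would be described rather than built into the primary model.

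If the sponsor prefers the pre-test, it should correct SAP section 5, and declare and justify the departure from the protocol in SAP section 8.

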7.6.2.2 Analysis of superiority to vehicle control

The analysis of superiority will be performed separately for the Test treatment versus the Vehicle treatment and for the Reference treatment versus the Vehicle treatment and separately for the inflammatory and non-inflammatory lesions. Each of these analyses will be performed using an ANOVA model with percent change from baseline in the lesion count as outcome and treatment, center and treatment-by-center interaction as factors. If the treatment-by-center interaction factor is not significant at the 0.05 level, the model will be rerun without the interaction term. The model will be fit on data from the Test and Vehicle treatment for analysis of superiority of the Test treatment and separately on data from the Reference and Vehicle treatment for analysis of superiority of the Reference treatment. From this model, the least square (LS) mean estimate for each treatment group with the 95% CI will be calculated; further, an estimate of the LS mean difference between the active treatment (Test or

Reference) and Vehicle with 95% CI and the p-value for test of no difference will be calculated.

Superiority will be established if the mean percent change from Baseline (reduction) for each active treatment and each lesion type is estimated to be greater than, and statistically significantly different from ($p < 0.05$ for test of no difference) that for the Vehicle, for the mITT population.

Analysis of superiority will be performed on the mITT population.

A non-parametric rank-based ANOVA will be considered under the same circumstances as for the analysis of bioequivalence.

7.6.3 Analyses of IGA

At each study visit, beginning at Visit 1, an Investigator will assess the overall status of the subject's face for acne vulgaris using the IGA on a scale from 0=Clear to 4=Severe. To be included in the study, subjects must have a definite clinical diagnosis of acne vulgaris of severity grade 2, 3, or 4 at screening/baseline.

Number and percentage of subjects at each IGA severity grade will be tabulated by visit. In addition, a shift table for changes in IGA grades from Baseline to each post-baseline visit will be created. This analysis will be performed for both mITT and PP populations.

7.7 Safety Analyses

7.7.1 Adverse Events

Adverse Events will be coded using the MedDRA version 25.0 AE coding system for purposes of summarization.

Only treatment-emergent adverse events (TEAEs) will be used for the summary analysis. An AE will be considered as treatment-emergent if the date of onset is on or after the date of the first study medication administration or if it increased in severity during the study treatment period. AEs with unknown start dates will be counted as treatment-emergent unless the AE resolution date is prior to the study drug start date. If the AE start date is partially missing, the

AE will be considered treatment-emergent, unless the month and year (when available) rule out the possibility that the event occurred post start of the study drug.

AE will be considered treatment-related if its relationship to study product is recorded as Possible, Probable or Definitely related. AEs with missing relationship will also be considered related.

An overall summary will include, by treatment group and overall, the number of TEAEs and the number and percentage of subjects reporting at least 1 TEAE in the following categories:

- Any AE
- Any TEAE,
- Treatment-related TEAE,
- Serious TEAE,
- TEAE leading to discontinuation of the study medication.
- Fatal AE

Count of AEs by severity and relationship to the study medication will also be presented.

The following TEAE frequency tables will be prepared summarizing the number and percentage of subjects reporting at least one TEAE by MedDRA system organ class (SOC) and preferred term (PT):

- All TEAEs
- Treatment-related TEAEs
- Serious TEAEs
- TEAE leading to discontinuation of the study medication
- TEAEs by maximum severity

A subject experiencing the same AE multiple times will only be counted once for that preferred term. Similarly, if a subject experiences multiple AEs within the same system organ class, that subject will be counted only once in that system organ class. In the summary by severity only the highest applicable severity will be chosen for each preferred term and system organ class.

Summaries of AEs will be presented in alphabetical order of SOC and preferred terms. Additionally, TEAEs will be summarized by the preferred terms in the descending order of frequency in the total treatment group. In this table a p-value from Fisher's exact test comparing event rates between the Test and the Reference treatment groups will be provided for those preferred terms that have frequency > 1% in either Test or Reference group.

All information pertaining to adverse events noted during the study will be listed by subject, detailing verbatim, preferred term, system organ class, start date, stop date, severity, outcome, action taken, and causal relationship to the study drug. The adverse event onset will also be shown relative (in number of days) to the date of first administration of the study medication. In addition, the adverse event duration (if AE Stop Date is available) will be evaluated as below and presented (in number of days).

$$\text{AE Duration} = \text{AE Stop Date} - \text{AE Start Date} + 1$$

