both using the modified intent-to-treat (mITT) study population and Last Observation Carried Forward (LOCF).

- An active treatment will be considered to be superior to the placebo if the difference in the means for the two treatment groups are statistically significant ($p < 0.05$) and the active treatment's mean percent reduction from screening/baseline is greater than that for placebo.
- Analysis of local irritation reactions (application site reactions).
- A descriptive analysis comparing the local irritation reactions (**application site reactions**) for each treatment group will be conducted to ensure that the test product is similar to the reference product with regard to the expected and unexpected application site reactions.
- Analysis of IGA scores:
 - Descriptive statistics using categorical methods to compare IGA Scores between each treatment group will be conducted and presented. No inferential analyses are planned.
- Summary of Subjects who terminate prematurely.
 - Reasons for premature termination will be summarized by treatment group.
- Concomitant medication.
 - The start and stop calendar date (e.g., mm/dd/yyyy) and study day (e.g., Day X) of concomitant medication used prior to and during the study will be provided in the data set in addition to the reason for the medication use. It should clearly be noted whether the medication was used prior to screening/baseline visit, during the study, or both.

Safety Analyses

Safety analyses will be conducted on the safety population. Safety Incidence of all adverse

events reported during the study will be summarized using the MedDRA dictionary by treatment group, body system, severity and relationship to study drug.

The report of AEs will include relatedness to treatment, date of onset, description of the AE, severity, action taken, outcome and date of resolution. Formal statistical evaluation(s) of the comparability of the two active treatment groups will be conducted with regard to the frequency and severity of any AE that occurs in at least 5% of the subjects in either active treatment group.

Application site reactions such as erythema, dryness, burning/stinging, erosion, edema, pain and itching will be summarized for the safety population by treatment group and study visit using frequencies and percentages of subjects.

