10.3.2 Safety Assessment

The extent of exposure will be summarized using descriptive statistics. No inferential analyses are planned.

Incidence of all adverse events reported during the study will be summarized using the MedDRA dictionary by treatment group, body system, severity, and relationship to study drug. The comparability of the Test and Reference treatment groups for the frequency and severity of any adverse event that occurs in at least 5% of the subjects in either treatment group will be evaluated using categorical methods.

The concomitant medications used will be summarized by treatment group.

Application site reactions such as erythema, dryness, burning/stinging, erosion, edema, pain and itching will be summarized for the safety population by treatment group and study visit using frequencies and percentages of subjects.

Safety analyses will be performed on the safety population. All safety data will be listed by treatment and Subject in data listings.

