Worsening of the disease under study will be measured by an increase in the IGA score by one or more grades, and should be recorded as an adverse event only if the presentation and/or outcome is more severe than would normally be expected from the normal course of the disease in a particular subject.

In this study, any adverse event occurring after the subject has signed the informed consent/assent form until the end of follow-up period should be recorded and reported as an adverse event.

A treatment-emergent AE (TEAE) is any AE that occurs after initiation of study medication, or any event already present that worsens in either intensity or frequency following exposure to study medication.

For adverse event recording, the study period is defined for each subject as that time period from signature of the informed consent/assent form through the end of the study (including the follow up period). All adverse events that occur during the defined study period must be recorded on the source documentation and CRF, regardless of the severity of the event or judged relationship to the study drug. For serious adverse events, the Serious Adverse Event Form must also be completed, and the serious adverse event must be reported immediately (see Section on Reporting below).

At each contact with the subject, the Investigator or designee must question the subject about adverse events by asking an open-ended question such as, “Have you had any unusual symptoms or medical problems since the last visit? If yes, please describe.” All reported or observed signs and symptoms will be recorded individually, except when considered manifestations of a medical condition or disease state. A precise diagnosis will be recorded whenever possible. When such a diagnosis is made, all related signs, symptoms, and any test findings may be recorded collectively as a single diagnosis on the CRF and, if it is a serious adverse event, also on the Serious Adverse Event Form.

The onset and end dates and times, action taken regarding study drug, treatment administered, and outcome for each adverse event must be recorded on the source documentation.

The relationship of each adverse event to study drug treatment, and the severity and seriousness of each adverse event, as judged by the Investigator, must be recorded as described below.

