11.1.2 Relationship to Study Medication

Adverse events will be assessed for the relationship to the study drug (causality) according to the following scale:

TERM	DEFINITION	CLARIFICATION
No Reasonable Possibility (not related)	This category applies to those adverse events which, after careful consideration, are clearly due to extraneous causes (disease, environment, etc.) or to those adverse events, which after careful medical consideration at the time they are evaluated, are judged to be unrelated to the test drug.	
• An adverse experience may be considered• No Reasonable Possibility if it is clearly due to extraneous causes or when (must have two):• It does not follow a reasonable temporal sequence from the administration of the test drug.• It could readily have been produced by the subject’s clinical state, environmental or toxic factors, or other modes of therapy administered to the subject.• It does not follow a known pattern of response to the test drug.• It does not reappear or worsen when the drug is re-administered.

Reasonable Possibility (related)	This category applies to those adverse events for which, after careful medical consideration at the time they are evaluated, a connection with the test drug administration cannot be ruled out with certainty or felt with a high degree of certainty to be related to the test drug.	
• An adverse experience may be considered Reasonable Possibility related if or when (at least two of the following):• It follows a reasonable temporal sequence from administration of the drug.• It could not be reasonably explained by the known characteristics of the subject’s clinical state, environmental or toxic factors, or other modes of therapy administered to the subject.• It disappears or decreases on cessation or reduction in dose. There are important exceptions when an adverse event does not disappear upon discontinuation of the drug, yet drug relatedness clearly exists.• It follows a known pattern of response to the test drug.
----------------------------------	--	---

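### The SAP's definition of a treatment-related AE uses causality grades that are not on the protocol's scale, and the protocol's Test–Reference comparison of AE severity is not planned

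*SAP*

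**What the plan says.** **Causality.** Protocol 11.1 says that the relationship, severity and seriousness of each AE, "as judged by the Investigator, must be recorded as described below". The scale that follows in 11.1.2 has two grades: No Reasonable Possibility, glossed as not related, and Reasonable Possibility, glossed as related.

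SAP 7.7.1 defines the analysis flag differently: "AE will be considered treatment-related if its relationship to study product is recorded as Possible, Probable or Definitely related". It adds that "AEs with missing relationship will also be considered related". The flag feeds two outputs: the treatment-related row of the overall AE summary and the treatment-related TEAE table by SOC and preferred term. A further output does not depend on the flag: "Count of AEs by severity and relationship to the study medication will also be presented".

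**Comparison of the active arms.** Protocol 10.3.2 requires AE incidence to be summarised "by treatment group, body system, severity, and relationship to study drug". The Safety Analyses part of the synopsis promises a formal statistical evaluation of the two active groups, which "will be conducted with regard to the frequency and severity of any AE that occurs in at least 5% of the subjects" in either active group. Protocol 10.3.2 repeats the commitment and says categorical methods will be used.

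SAP 7.7.1 plans a Fisher's exact test of Test against Reference event rates for preferred terms above 1% in either group. Severity appears in a table of TEAEs by maximum severity, with treatment columns under SAP 7.1, and in the counts. No between-group comparison of severity is named. SAP 8 declares an expanded mITT definition and says that nothing else departs from the protocol.

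**The concern.** The SAP rule tests for values that the protocol gives investigators no means of recording. Missing causality is also routed to related, so a literal reading produces a perverse result: an AE with no causality entry is counted as related, and an AE the investigator actively judged related is not.

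This matters because comparing the safety of Test, Reference and Placebo is a stated protocol objective (Protocol 2). Under Protocol 6.3, local irritation becomes an AE only if it worsens significantly, needs medical intervention or leads to discontinuation. The AE tables therefore carry the more consequential skin reactions, and for those reactions relatedness and severity are what a reader comparing a generic with its reference will look for.

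The second gap is a protocol commitment that the SAP drops without saying so. A reader relying on SAP 8 would believe the AE analyses match the protocol.

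**Working it through.** The plan gives no figure to reproduce on this point. The check sets the rules side by side and adds a short calculation on the thresholds.

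**Step 1: overlap of the causality categories.**

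| Recorded value (Protocol 11.1.2) | In the SAP related set {Possible, Probable, Definitely related, missing}? | Flag under the SAP rule |
|---|---|---|
| No Reasonable Possibility (not related) | No | Not related |
| Reasonable Possibility (related) | No | Not related |
| Missing | Yes | Related |

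Of the SAP's 3 named grades, 0 match either of the protocol's 2 grades. The only route to a related flag is a missing entry.

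**Step 2: is there a mapping or a version explanation?** Neither document contains a mapping, and the text is not redacted at either place. The SAP is written against protocol version 2.0, and the specific changes in that version's revision history do not touch causality.

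**Step 3: which outputs are affected?** The treatment-related row of the overall summary and the treatment-related SOC/PT table use the flag. Of the TEAE tables the SAP lists by SOC and PT, the treatment-related table is the only one that uses relationship. The count of AEs by severity and relationship and the by-subject listing use the recorded value, so they survive. The SAP does not say that the count is broken down by SOC or PT.

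**Step 4: the Test–Reference comparison.**

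| | Protocol (synopsis; 10.3.2) | SAP 7.7.1 |
|---|---|---|
| Frequency | Compared, AEs in ≥5% of either active group | Fisher's exact test, terms >1% in either active group |
| Severity | Compared, same AEs | Maximum-severity table, no comparison |

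**Step 5: does the changed threshold lose any frequency test?** Arm sizes are redacted, so n per arm is an assumption, shown from 100 to 500. The minimum number of subjects is floor(0.01n) + 1 for above 1%, and ceil(0.05n) for at least 5%.

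| n per arm (assumed) | >1% | ≥5% |
|---|---|---|
| 100 | 2 | 5 |
| 200 | 3 | 10 |
| 300 | 4 | 15 |
| 400 | 5 | 20 |
| 500 | 6 | 25 |

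Any term at 5% or more is also above 1%, whatever n is. No protocol-specified frequency test is lost. What is lost is the severity comparison: SAP 7.7.1 plans none.

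**The case against.** The strongest reply is that nobody would issue the literal table. The protocol grade carries the word related in its own label, and the SAP is inclusive enough to count missing causality as related, so a programmer would query the rule or map the grade. That is likely, but the mapping would then be an undocumented choice about a rule the SAP is meant to fix.

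A second reply is that the eCRF is not among the documents and may offer Possible, Probable and Definite. If so, the SAP rule works on the collected data and nothing drops out. This is a real limit on how certain the reporting consequence is. It does not remove the inconsistency: the eCRF would then contradict Protocol 11.1.2, and the documents would still need reconciling.

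Third, recorded causality is kept in the counts and listings, and the list of factors in Protocol 10.3.2 does not clearly demand a body-system-by-relationship cross-table. Both points are fair, but the SAP plans such a table and its definition would populate it wrongly.

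Fourth, this protocol uses categorical methods elsewhere (10.3.3.4 and 10.3.3.5) for purely descriptive comparisons, so the maximum-severity table might be thought to satisfy 10.3.2. The synopsis rules that reading out, because it promises a formal statistical evaluation of severity as well as frequency.

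Finally, local irritation is scored 0 to 3 at every visit and tabulated by severity, with shifts from baseline (SAP 7.7.4). That reduces the practical loss for local tolerability. It does not replace the comparison promised for AEs.

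**Conclusion.** The point holds on both parts and should be corrected. The mismatch between the causality rule and the protocol scale is certain from the text. The consequence, treatment-related outputs holding only AEs with missing causality, assumes that the data follow the protocol scale and that the SAP rule is applied literally. The missing severity comparison does not depend on those assumptions. The move from 5% to 1% for frequency does no harm in itself but is undeclared, so the SAP 8 statement of no further changes is incorrect for the AE analyses. The effect is confined to safety reporting and does not reach the equivalence or superiority conclusions.

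**What to change.** 1. Check the causality field on the AE eCRF page. If it carries the protocol's two grades, rewrite the SAP 7.7.1 rule so that an AE is treatment-related when recorded as Reasonable Possibility (related) or when causality is missing. If it carries other grades, reconcile the eCRF with Protocol 11.1.2 first and state the mapping in the SAP.
2. Add a categorical Test–Reference comparison of AE severity for AEs occurring in at least 5% of either active group, as the protocol specifies.
3. Keep the above-1% threshold for the Fisher test if preferred, and declare it in SAP 8 as a change from the protocol.

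The cost is a few lines of SAP text, one eCRF check and one added comparison. Data collection does not change if the eCRF already follows the protocol scale.
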